### 3.4.2 Visit schedule

**Table 3-4 Evaluation and visit schedule**

Examination	Screening/ Baseline	Week									
		4	16	32	52	64	80	96	112	128	144
Informed consent	X										
No Evidence of Disease	X										
Inclusion/exclusion criteria	X										
Tissue Biopsy	X										
Radiographic assessment	X										
Physical examination	X										
ECG	X										
Laboratory test	X	X	X	X	X	X	X	X	X	X	X
Research Blood Draw	X	X	X		X						
HBV-DNA, HbsAg, HBs Ab, HBs Ab, HCV-RNA-PCR^6	X										
Patient Questionnaire	X										
Follow Up Form^8		X	X	X	X	X	X	X	X	X	X

See Section 3.2.2

See Section 3.4.7; Tissue biopsy must have been obtained PRIOR to curative intent therapy

Baseline radiographic assessment (CT, PET-CT, PET and/or MRI as appropriate) must be preformed within 12 weeks of starting everolimus. CT, PET-CT, PET and/or MRI as appropriate should be performed at least every 4-6 months in years 1 and 2 then every 6 months in year 3.

Baseline assessments must be performed within 7 days of starting everolimus. Hemoglobin, platelets, total white blood cell count (WBC), and differential; sodium, potassium, chloride, bicarbonate, calcium, glucose, creatinine, blood urea nitrogen, albumin, total protein, SGOT (AST), SGPT (ALT), total bilirubin, alkaline phosphatase, uric acid, phosphorus, serum lipid profile (triglycerides, total cholesterol, HDL and LDL); PT (INR) evaluation only at baseline unless otherwise indicated. Patients should be fasting at the time of the blood sampling.

Blood draw for serum, whole blood and optional PBMC isolation (see Section 3.4.7). Serum will be drawn at screening, weeks 4, 16 and 52. Whole blood will be drawn at weeks 4, 16 and 52. Optional PBMC will be drawn at screening and week 4.

All patients should be **screened** for hepatitis risk factors and any past illnesses of hepatitis B and hepatitis C infection. If the patient has any of the risk factors outlined in section 3.4.1 then serologic testing must be done.

All patients should fill out the Patient Questionnaire prior to first dose. See the Study Procedures manual.

See the Study Procedures Manual

### **3.4.3 Efficacy assessments**

The primary study endpoint is progression-free survival. Disease progression will be evaluated by clinical and radiographic methods and date of progression will be recorded. If in question, disease progression should be confirmed pathologically. Site of disease progression will be classified as local (progression at primary tumor site), regional (progression in cervical lymph nodes), and/or distant (metastatic disease).

A diagnosis of second primary tumor must be confirmed pathologically. Deaths on study should be classified as disease (SCCHN), non-disease, or study treatment related.

### **3.4.4 Safety assessments**

Safety assessments will consist of monitoring and recording all adverse events and serious adverse events, the regular monitoring of hematology, blood chemistry and urine values, regular measurement of vital signs and the performance of physical examinations.

These assessments should be performed within  $\pm 2$  days of the scheduled day of assessment except for adverse events that will be evaluated continuously through the study. Safety and tolerability will be assessed according to the NIH/NCI CTC [http://evs.nci.nih.gov/ftp1/CTCAE/CTCAE\\_4.03\\_2010-06-14\\_QuickReference\\_5x7.pdf](http://evs.nci.nih.gov/ftp1/CTCAE/CTCAE_4.03_2010-06-14_QuickReference_5x7.pdf).

#### **3.4.4.1 Adverse events**

Information about all adverse events, whether volunteered by the subject, discovered by investigator questioning, or detected through physical examination, laboratory test or other means, will be collected and recorded and followed as appropriate.

An adverse event is the appearance or worsening of any undesirable sign, symptom, or medical condition occurring after starting the study drug even if the event is not considered to be related to study drug. Medical conditions/diseases present before starting study drug are only considered adverse events if they worsen after starting study drug. Abnormal laboratory values or test results constitute adverse events only if they induce clinical signs or symptoms, are considered clinically significant, or require therapy.

The occurrence of adverse events should be sought by non-directive questioning of the patient at each visit during the study. Adverse events also may be detected when they are volunteered by the patient during or between visits or through physical examination, laboratory test, or other assessments. As far as possible, each adverse event should be evaluated to determine:

1. the severity grade (mild, moderate, severe) or (grade 1-4)
2. its relationship to the study drug(s) (suspected/not suspected)
3. its duration (start and end dates or if continuing at final exam)

4. action taken (no action taken; study drug dosage adjusted/temporarily interrupted; study drug permanently discontinued due to this adverse event; concomitant medication taken; non-drug therapy given; hospitalization/prolonged hospitalization)
5. whether it constitutes a serious adverse event (SAE)

Grading for all adverse events will utilize NCI CTCAE v4.0.

CTCAE version 4.0 is available at: <http://ctep.cancer.gov/reporting/ctc.html>

All adverse events should be treated appropriately. Such treatment may include changes in study drug treatment including possible interruption or discontinuation, starting or stopping concomitant treatments, changes in the frequency or nature of assessments, hospitalization, or any other medically required intervention. Once an adverse event is detected, it should be followed until its resolution, and assessment should be made at each visit (or more frequently, if necessary) of any changes in severity, the suspected relationship to the study drug, the interventions required to treat it, and the outcome.

Information about common side effects already known about the investigational drug can be found in the [Investigators' Brochure](#). This information should be included in the patient informed consent and should be discussed with the patient during the study as needed.

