Everolimus has shown activity in patients whose metastatic renal cell cancer has progressed despite treatment with VEGF-R inhibitors in a phase 2 study . A Phase III, randomized, double blind, placebo controlled study in patients with mRCC who progressed on a VEGFR TKI demonstrated that everolimus, administered daily at an oral dose of 10 mg provides positive clinical benefit . Median progression free survival (PFS) was prolonged from 1.87 months for patients receiving placebo to 4.01 months for everolimus treated patients, assessed by central independent review blinded to clinical data (hazard ratio 0.30, 95% CI 0.22-0.40, p<0.0001).

Overall, the most frequent mild-moderate Grade 1/2 adverse effects have been rash, stomatitis, fatigue, neutropenia and to a lesser extent gastrointestinal disorders (nausea, anorexia, diarrhea, vomiting), and headache. The primary DLT has been severe (Grade 3) stomatitis, and occasionally fatigue, hyperglycemia, and neutropenia. Reduced blood counts, hyperlipidemia (mainly hypercholesterolemia) and hyperglycemia are relatively frequent laboratory findings. Infections have not been notably frequent or severe. Non-infectious low-Grade (Grade 1/2) pneumonitis has led to development of treatment guidelines for the disorder (Table 3-2). Preliminary indications of anti-tumor activity are encouraging.

For more information on known undesirable effects of Everolimus refer to Section 3.2.5.

Further detailed information regarding Everolimus clinical development, safety and efficacy is provided in the [Investigator's Brochure](#).

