### Secondary

- Toxicity of everolimus versus placebo as adjuvant therapy
- Site of disease progression (locoregional vs. distant) in subjects treated with everolimus versus placebo
- Incidence of second primary tumors in subjects treated with everolimus versus placebo
- Prevalence of Akt/mTOR pathway activation in locally advanced SCCHN
- Determine correlation between progression free survival (PFS) and the degree of activation of the Akt/mTOR pathway biomarkers in tumors and adjacent mucosa treated with everolimus versus placebo
- Determine if PTEN status is predictive marker of Everolimus sensitivity

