### **3.2.5.1 Management of stomatitis/oral mucositis/mouth ulcers**

Stomatitis/oral mucositis/mouth ulcers due to Everolimus should be treated using local supportive care. Please note that investigators in earlier trials have described the oral toxicities associated with Everolimus as mouth ulcers, rather than mucositis or stomatitis. If your examination reveals mouth ulcers rather than a more general inflammation of the mouth, please classify the adverse event as such. Please follow the paradigm below for treatment of stomatitis/oral mucositis/mouth ulcers:

1. For mild toxicity (Grade 1), use conservative measures such as **non-alcoholic mouth wash or salt water (0.9%) mouth wash** several times a day until resolution.
2. For more severe toxicity (Grade 2 in which case patients have pain but are able to maintain adequate oral alimentation, or Grade 3 in which case patients cannot maintain

adequate oral alimentation), the suggested treatments are **topical analgesic mouth treatments (i.e., local anesthetics such as benzocaine, butyl aminobenzoate, tetracaine hydrochloride, menthol, or phenol) with or without topical corticosteroids**, such as triamcinolone oral paste 0.1% (Kenalog in Orabase®).

3. Agents containing hydrogen peroxide, iodine, and thyme derivatives (e.g. Thymol) may tend to worsen mouth ulcers. It is preferable to avoid these agents.
4. Antifungal agents must be avoided unless a fungal infection is diagnosed. In particular, systemic imidazole antifungal agents (ketoconazole, fluconazole, itraconazole, etc.) should be avoided in all patients due to their strong inhibition of Everolimus metabolism, thereby leading to higher Everolimus exposures. Therefore, topical antifungal agents are preferred if an infection is diagnosed. Similarly, antiviral agents such as acyclovir should be avoided unless a viral infection is diagnosed.

Note: Stomatitis/oral mucositis should be appropriately graded using the functional grading given on the NCI-CTC for adverse events, version 3.0.

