## 6 Statistical methods

### 6.1 Statistical methods

This is a multicenter, randomized, placebo-controlled, double-blind Phase II clinical trial of adjuvant Everolimus vs. placebo. Patients will be randomized 8-16 weeks after the completion of curative intent therapy. The primary endpoint is 2-year progression-free survival (PFS) rate. Progression-free survival will be estimated using the method of Kaplan-Meier, and compared between the two treatment arms using the stratified logrank test. Multivariate regression models will be used to compare treatment effect between treatment groups adjusting for other important prognostic factors. Adverse event rates will be summarized and compared between treatment groups using Chi-squared or Fisher's exact test. Continuous variables will be compared between groups using t-test or Wilcoxon rank sum test as appropriate, and categorical variables will be compared using Cox Regression Analysis. Regression models will be used as part of exploratory analysis to explore treatment effects adjusting for other important prognostic factors. The guideline to stop early for futility will be if the conditional power at the interim look (Section 4.7) is less than 10% using the stochastic curtailment approach (as described in Jennison and Turnbull).

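### Toxicity is compared only through adverse event rates, which count a laboratory abnormality only if it is symptomatic, judged significant or treated, so absolute laboratory toxicity may be understated

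*Combined protocol and SAP*

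**What the plan says.** All references are to the combined protocol and SAP.

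- **Objective.** Section 2 lists first among the secondary objectives: "Toxicity of everolimus versus placebo as adjuvant therapy". It does not define toxicity further.
- **Analysis.** Section 6.1: "Adverse event rates will be summarized and compared between treatment groups using Chi-squared or Fisher's exact test". It also says: "Continuous variables will be compared between groups using t-test or Wilcoxon rank sum test as appropriate", but does not name laboratory values there. No tabulation of laboratory values by grade is specified.
- **Counting rule.** Section 3.4.4.1: "Abnormal laboratory values or test results constitute adverse events only if they induce clinical signs or symptoms, are considered clinically significant, or require therapy". It gives no criterion for clinical significance and does not say who decides.
- **Expected effects.** Section 1.1.3.3: "Reduced blood counts, hyperlipidemia (mainly hypercholesterolemia) and hyperglycemia are relatively frequent laboratory findings". Section 3.2.5 adds reduced hemoglobin, lymphocytes, platelets and neutrophils, and raised creatinine.
- **Severity.** Item 1 of the evaluation list in Section 3.4.4.1 asks for "the severity grade (mild, moderate, severe) or (grade 1-4", while the same section later states: "Grading for all adverse events will utilize NCI CTCAE v4.0".

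**The concern.** The plan expects this drug to change laboratory values and draws them on a fixed schedule. The only toxicity comparison it specifies nevertheless sees those values through a filter of symptoms, judgement or treatment. At several centers with no common criterion, the same platelet count or glucose could be an adverse event at one site and not at another.

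The patients have no evidence of disease and take study drug for up to a year. The absolute excess of toxicity over placebo is therefore what a reader would weigh against any gain in progression-free survival. A filter that passes only a fraction of occurrences lowers both arms' rates, and in absolute terms it lowers the higher rate more.

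**Working it through.** The plan states no laboratory toxicity rate and no power for the toxicity comparison, so there is no figure to reproduce. The check is a comparison of sections, followed by an illustration on assumed rates.

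**1. Can a measured abnormality that matters stay out of the comparison?**

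- Table 3-1 (Section 3.2.3) acts on measured counts alone. Grade 2 thrombocytopenia (platelets below 75 and at least 50 × 10⁹/L) and grade 3 neutropenia (neutrophils below 1 and at least 0.5 × 10⁹/L) both lead to interruption, with or without symptoms.
- Section 3.2.4 requires at least weekly follow-up after interruption or discontinuation, and names an abnormal laboratory value as a cause alongside an adverse event.
- The discontinuation reasons after Table 3-5 (Section 3.2.5.3) list adverse events and abnormal laboratory values as separate items.
- Section 3.4.4.1 does not say that a value leading to interruption is thereby an adverse event.

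The protocol thus provides for a patient interrupted or stopped for a laboratory value that is not classed as an adverse event. Under Section 6.1 that patient need not appear in the comparison.

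**2. Are the values available?**

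Table 3-4 (Section 3.4.2) marks laboratory tests at baseline and at ten later visits. Treatment lasts at most 1 year (Sections 3.1 and 3.3.1), so four of the ten (weeks 4, 16, 32 and 52) fall within it and six (weeks 64 to 144) come after. The weekly follow-up under Section 3.2.4 would add unscheduled values.

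**3. What does partial capture do?**

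Let p₁ and p₀ be the true rates on everolimus and placebo, and let c be the fraction of occurrences recorded as adverse events, taken as equal in the two blinded arms.

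- Observed difference = c·(p₁ − p₀), which shrinks with c.
- Observed ratio = c·p₁ / c·p₀ = p₁/p₀, which does not change.
- Chi-squared power, two-sided 0.05, n = 80 per arm (Section 3.2.1) = Φ{[Δ − 1.96·√(2p̄(1−p̄)/n)] / √[(p₁(1−p₁) + p₀(1−p₀))/n]}, with observed rates put in for p₁ and p₀, Δ their difference and p̄ their mean.

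Worked case, assumed true rates 30% v 10%, c = 0.5. Observed rates are 15% and 5%, so Δ = 0.10 and p̄ = 0.10.

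- Null term: 1.96·√(0.18/80) = 0.0930.
- Denominator: √[(0.1275 + 0.0475)/80] = 0.0468.
- Power = Φ[(0.10 − 0.0930)/0.0468] = Φ(0.15) = 0.56.

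Fisher power was found by exact enumeration.

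| Assumed true rates | c | Difference (points) | Ratio | Chi-squared power | Fisher power |
|---|---|---|---|---|---|
| 30% v 10% | 1 | 20 | 3 | 0.89 | 0.87 |
| | 0.75 | 15 | 3 | 0.76 | 0.71 |
| | 0.5 | 10 | 3 | 0.56 | 0.48 |
| | 0.25 | 5 | 3 | 0.30 | 0.17 |
| 20% v 5% | 1 | 15 | 4 | 0.83 | 0.79 |
| | 0.75 | 11.3 | 4 | 0.69 | 0.62 |
| | 0.5 | 7.5 | 4 | 0.50 | 0.37 |
| | 0.25 | 3.8 | 4 | 0.27 | 0.10 |

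Every rate and capture fraction in this table is an assumption; only the 80 per arm comes from the plan.

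**The case against.** The rule has three alternative routes, and the consequential abnormalities will often pass one of them. Grade 3 hyperlipidemia is to be managed medically (footnote to Table 3-1), so it counts as treated. A count that forces interruption appears in Table 3-1 under hematological toxicity, and it would be odd to call it insignificant. Interruptions must be recorded in any case. Section 3.4.4 makes laboratory monitoring a safety assessment in its own right. Limiting laboratory adverse events to those with consequences is a legitimate definition that applies equally to both arms.

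Most of this stands. It means that what escapes is probably weighted toward symptom-free, untreated changes that do not alter dosing, and that a loss cannot be asserted as fact. It does not close the gap. The text never makes a dose-interrupting value an adverse event, it names the two separately in two places, and Section 6.1 provides no other toxicity comparison that would show the values by grade.

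A reader might also infer that the severity item adds to the undercount, because its scales stop at severe or at grade 4. It cannot: a scale grades events already counted. Nor is the scale left open, since the same section prescribes CTCAE v4.0 for all adverse events. Fatal events are covered by the serious adverse event definition and the grade 4 and 5 reporting columns in Section 3.4.4.2, and by the classification of deaths in Section 3.4.3.

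**Conclusion.** The point holds as a possibility and as a low-cost improvement. As specified, the toxicity comparison may understate absolute laboratory toxicity and the absolute difference between arms. The documents give neither laboratory toxicity rates nor the share that the rule would leave out, so the size is unknown. The table above shows only how the loss would scale.

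Two stronger readings are not supported. One is that laboratory toxicity is certain to be undercounted; that depends on how sites apply the significance route. The other is that the comparison is biased in relative terms. The rule is the same in both blinded arms, and with equal capture the risk ratio is unchanged. Unequal capture would need evidence that the documents do not contain.

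The severity item is a separate inconsistency of wording with no effect on the laboratory count.

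**What to change.** 1. Keep the Section 3.4.4.1 definition for adverse event reporting.
2. Add to Section 6.1 a by-arm comparison of worst on-treatment CTCAE v4.0 grade and shift from baseline, derived from all measured laboratory values whether or not an adverse event was reported. Use the draws at baseline and weeks 4, 16, 32 and 52, plus unscheduled values such as those from the weekly follow-up in Section 3.2.4. Show a scheduled-only version beside it, since that extra follow-up may fall unevenly between arms.
3. As a separate wording correction, have item 1 of the evaluation list in Section 3.4.4.1 ask for CTCAE v4.0 grade 1-5, in line with the governing sentence of that section and the grade 5 columns in Section 3.4.4.2. Section 3.2.5.1 points to another version ("Stomatitis/oral mucositis should be appropriately graded using the functional grading given on the NCI-CTC for adverse events, version 3.0"), and the two passages must be reconciled.

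The cost is one additional table and a one-line edit, with no extra tests. The values must be captured on the CRF. Section 5.1 says only that forms will cover the required data elements, and the forms are not part of the documents, so this needs to be confirmed.

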#### 3.4.4.2 Serious adverse events

A serious adverse event is an undesirable sign, symptom or medical condition which:

- is fatal or life-threatening
- results in persistent or significant disability/incapacity
- constitutes a congenital anomaly/birth defect
- requires inpatient hospitalization or prolongation of existing hospitalization, unless hospitalization is for:
  - routine treatment or monitoring of the studied indication, not associated with any deterioration in condition (specify what this includes)
  - elective or pre-planned treatment for a pre-existing condition that is unrelated to the indication under study and has not worsened since the start of study drug
  - treatment on an emergency outpatient basis for an event not fulfilling any of the definitions of a SAE given above and not resulting in hospital admission
  - social reasons and respite care in the absence of any deterioration in the patient's general condition
- is medically significant, i.e., defined as an event that jeopardizes the patient or may require medical or surgical intervention to prevent one of the outcomes listed above
- Pregnancy

To ensure patient safety, the principal investigator has the obligation to report all serious adverse events to the FDA, IRB, and Novartis, **regardless of suspected causality**, occurring:

- after the patient has provided informed consent and until 30 days after the patient has stopped study treatment/participation

- after the patient is randomized and until 30 days after the patient has stopped study treatment/participation
- after the patient begins taking study drug and until 30 days after the patient has stopped study treatment/participation
- after protocol-specified procedures begin (e.g., placebo run-in, washout period, double-blind treatment, etc.) and until 30 days after the patient has stopped study treatment/participation
- after the start of any period in which the study protocol interferes with the standard medical treatment given to a patient (e.g., treatment withdrawal during washout period, change in treatment to a fixed dose of concomitant medication) and until 30 days after the patient has stopped study treatment/participation

SAEs must be reported to Novartis within 24 hours of learning of its occurrence. Any SAEs experienced after this 30 day period should only be reported to Novartis if the investigator suspects a causal relationship to the Novartis study drug. Recurrent episodes, complications, or progression of the initial SAE must be reported as follow-up to the original episode within 24 hours of the investigator receiving the follow-up information. An SAE occurring at a different time interval or otherwise considered completely unrelated to a previously reported one should be reported separately as a new event.

The investigator must assess and record the relationship of each SAE to each specific study drug (if there is more than one study drug), complete the SAE Report in English, and send the completed, signed form by fax as specified in Section 4.6. The original copy of the SAE Report and the fax confirmation sheet must be kept within the Trial Master File at the study site.

Follow-up information is sent to the same person to whom the original SAE Report Form was sent, using a new SAE Report Form stating that this is a follow-up to the previously reported SAE and giving the date of the original report. Each re-occurrence, complication, or progression of the original event should be reported as a follow-up to that event regardless of when it occurs. The follow-up information should describe whether the event has resolved or continues, if and how it was treated, whether the blind was broken or not (if applicable), and whether the patient continued or withdrew from study participation.

If the SAE is not previously documented in the [Investigator's Brochure](#) or Package Insert (new occurrence) and is thought to be related to the Novartis study drug, a Clinical Safety and Epidemiology Department associate may urgently require further information from the investigator for Health Authority reporting. Novartis may need to issue an Investigator Notification (IN), to inform all investigators involved in any study with the same drug that this SAE has been reported. Suspected Unexpected Serious Adverse Reactions (SUSARs) will be collected and reported to the competent authorities and relevant ethics committees in accordance with Directive 2001/20/EC or as per national regulatory requirements in participating countries.

All events reported to the FDA by the investigator are to be filed utilizing the Form FDA 3500A (MedWatch Form). Reporting guidelines are provided in the following table:

UNEXPECTED EVENT		EXPECTED EVENT	
GRADES 2 – 3 Attribution of Possible, Probable or Definite	GRADES 4 and 5 Regardless of Attribution	GRADES 1 - 3	GRADES 4 and 5 Regardless of Attribution

Written report within 10 working days. (Grade 1 SAE Reporting NOT required.) Any pregnancy should be reported as specified under Unexpected Grade 4 and 5 events.
	
Report by phone to University of Chicago Study Coordinator and University of Chicago Cancer Clinical Trials Office within 24 hours. Information will be distributed to Principal Investigators, University of Chicago IRB, and Novartis within 24 hrs. Written report to follow within 5 calendar days.
 
This includes all deaths within 30 days of the last dose of treatment regardless of attribution.
 
Any late death attributed to the agent (possible, probable, or definite) should be reported within 5 calendar days.
	
Adverse Event Expedited Reporting NOT required.
	
Written report, within 10 working days except for deaths within 30 days of the last dose of treatment regardless of attribution, which must be reported within 5 calendar days.
 
Any late death attributed to the agent (possible, probable, or definite) should be reported within 5 calendar days.

